2.2 Procedure

2.2.1 Study design, interventions and comparators

To provide the most robust causal inferences while minimising bias, we will conduct a randomised controlled trial (as recommended by the Magenta Book) for impact evaluation. In the RCT, we will compare various outcomes of interest across different time points between the aforementioned financial incentive intervention groups with the control (no financial incentives) group.

All participants, regardless of the treatment conditions, will get access to the "Better Health: Rewards" App developed by HUL and receive a wearable tracker if needed. The App is a mobile application that provides users with personalised health tracking services, offering them health-promoting feedback based on real-time monitoring (via the wearable) of their physical activities, sleep, and psychophysical indicators. The app can be paired up with mainstream wearable devices, including Apple Watch, Fitbit, Garmin, Google Fit, and HeadUp's own wearable, branded "Better Health: Rewards fitness tracker".

Our proposed trial is designed so that participants assigned to the *control group* will have an experience that is identical to that of users in the intervention groups, *except for the financial incentives themselves that are* contingent on their diet and PA

behaviours. This means that our comparison group is an 'active control group' because having access to wearables and the app may induce behaviour change.

Participants in the intervention group will receive one of three versions of the financial incentive intervention outlined below - which will only differ in the size of the rewards. Participants assigned to the *three intervention groups* will similarly receive a wearable and a version of the pilot app which enables measuring of physical activity and diet-related behaviours, together with redeeming of low-, medium-, and high-value in-app incentives, respectively (see Table 1).

Trial arms	Access to PA measurement / surveys via the app	Access to app content such as nudges and goal-setting	Access to wearable device if needed	Access to financial incentives contingent to behavioural change
Control group	Yes	Yes	Yes	No
Treatment group 1 - Low value incentive	Yes	Yes	Yes	Yes - Low value
Treatment group 2 - Medium value incentive	Yes	Yes	Yes	Yes - Medium value
Treatment group 3 - High value incentive	Yes	Yes	Yes	Yes - High value

The choice to provide control group participants with an experience that is identical to that of users in the intervention groups, except for the financial incentives themselves, has three core advantages:

- **Isolating the effect of the incentives:** the core question of the programme is whether *financial incentives in the context of the app* can improve health behaviours (on top of the app on its own), not whether financial incentives combined with a wider digital behavioural intervention can promote health behaviours. Offering access to the app and the wearable device to participants in the control group will enable us to better isolate the impact of financial incentives.
- Evaluation feasibility: Offering an engaging app experience and a wearable device worth £39 to the control group minimises the risk of a high dropout rate in the control group, which would otherwise make the evaluation challenging from a feasibility perspective.

• Marketing and engagement: Offering an engaging app experience and a wearable device to the control group would help to engage people in the scheme and make it easy for the marketing campaign to position the scheme as an appealing health promotion offer across all study arms: at a minimum all participants will receive a free wearable device worth £39 and an engaging app experience.

2.2.2 Setting and recruitment

2.2.2.1 Recruitment target and timeline

This study will be conducted in the local authority (LA) of Wolverhampton. Participants will be adults recruited from the community in Wolverhampton through an engagement and marketing campaign led by HUL.

The user recruitment period will last 6 to 8 weeks depending on the pace of recruitment, starting in February 2023. During week 6 of recruitment, uptake will be evaluated and a decision will be made whether to extend the recruitment window by 2 weeks.

During the recruitment period, HUL aims at having about 25,800 users starting the onboarding phase (see the Section 2.4 power calculation for more details). During the onboarding phase, a user downloads the app, signs up, and provides consent to participate in the study. By the end of week 6, or week 8 in case of slow recruitment, the recruitment window closes, meaning anyone who has not completed the onboarding process by then cannot take part in the study.

Since the marketing and acquisition campaigns will predominantly be deployed through online marketing, participants are likely to have clicked a link from their phone to the app store listing. From there, they can download the app for free.

For offline campaigns, a QR code will be used to direct people to the app store listing directly to maximise conversion. Prospective participants can also search the App Store / Google Play for the app.

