2.2.2.2 Providing informed consent

After an initial set of app-orientation screens explaining what the app is about, participants provide informed consent to participate in the study. As part of the consent process, interested users will be asked to read a participant information sheet and agree (or not agree) to:

• Take part in a study in which they will be randomly allocated to a control or a financial incentive intervention.

- Being contacted for research purposes (e.g. interviews being conducted as part of the implementation and process evaluation).
- Have their data shared with BIT to allow for data analysis.

Participants not providing informed consent will be excluded from the trial. Consent forms will be provided as part of the documentation for the ethical approval process. Consented users are subsequently asked to confirm they are over 18 years old and to the privacy notice and Terms of Service relating to the app. They may also optionally subscribe to 'reminder' emails from the app about their progress and other features. Users may unsubscribe from these communications at any time in the app.

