If participants' self-assessment indicates that they are eligible, they will proceed to the second stage of screening, otherwise their sign-up will end and they will not be able to use the app further, nor be included in the trial. Once a participant has provided informed consent, registered, and confirmed they meet the eligibility criteria, their onboarding phase ends and their baseline phase starts, which is elaborated in the next section.

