2.2.3 Baseline phase

The baseline period is specific to each user. It starts the day the user has been positively assessed for eligibility (passes eligibility criteria). This can be any day within the recruitment period. It ends when the recruitment window closes:

- Participants cannot complete baselining if they do not respond to at least one 24-hour dietary recall using Intake24⁸. The second intake24 is optional; users are encouraged to complete the second one within 3 days – this 3-day window is intended to streamline the onboarding experience for participants and provide a sufficient time period for participants to complete a second Intake24, while reducing the risk that the participants' baselining period is unduly protracted (which may add to abandonment-risk).
 
- Participants cannot complete baselining if they do not connect a wearable device; the (physical activity) challenges require at least 5 days of data⁹ during the baseline period. A day of data constitutes a day in which at least one step is registered. To calculate the baseline physical activity (PA), the first day is excluded as it is assumed that the data is partial only on the first day.
- Participants answer a food frequency questionnaire which will be used to create personal diet challenges (please see HUL's intervention design plan for more detail).

Their baseline period ends when this happens, and they enter randomisation

During this time:

- Participants indicate whether they need a wearable device and they receive it via mail;
- Participants may complete optional survey instruments (mental health, how they heard about the programme, education survey, motivations to change, disability survey);
- Participants provide the baseline data that HUL requires to fine-tune and personalise the incentive scheme (see the design protocol developed by HUL for more details);
- Participants provide the baseline outcome data that BIT requires for evaluation:
 - At least one Intake24 recall, to measure baseline dietary intakes;

⁸ Intake24 is a web-based self-completed 24-hour dietary recall system and has been widely used in national food and nutrition surveys.

⁹ Users exercise minutes and heart rate (HR) data are not required during the baseline period.

- Physical activity data for 5 days by the wearable device¹⁰;
- Sleep quality data and mental health (note: providing these data is not a prerequisite for entering randomisation)

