¹⁰ Note that a minimum of 4 valid days of physical activity data are required for inclusion in the evaluation. The first of the 5 days of data collected at baseline is therefore excluded from the evaluation as it is assumed to be a partial day. A valid day of data is one for which there is at least 6 hours of device wear time. This is explained in section 2.6 Data collection, management, and analysis ¹¹ BIT and HUL acknowledge that the risk of attracting too many users is also present. In this case, HUL will collect the same data as currently proposed during onboarding /registration (i.e. email, name, DOB, BMI, consent, gender etc) from the 'extra' users who will be invited to take part in the pilot. The app will limit the total number of registered users to 31,500. Once this number has been reached, users will see a message before they sign up, alerting them that the pilot is full and no more registrations are permitted, nor data captured.

¹² For the aim of the evaluation we do not consider the wearable a financial incentive (as part of the scheme), as the wearables will be provided to both the intervention and control group primarily to measure physical activity. Providing the wearable to both the intervention and control group will allow us to isolate the effects of providing financial rewards that are contingent on behaviour change. However, we acknowledge that users' behaviour will be affected by the presence of a wearable device.

Before the trial	Recruitment	Testing and fine-tuning of recruitment materials via UX research and online RCTs.	HUL, BIT supported with one online RCT
Before the trial	Baseline phase	Testing and fine-tuning the onboarding phase via UX and acceptability user testing research. This includes minimising the number of questions users are asked during the onboarding phase (for the evaluation and the fine-tuning of the scheme).	HUL
Before the trial	Baseline phase	Make data collection easy and attractive: (i) Adopt reminders to encourage data collection; (ii) Display the Intake24 survey link prominently on the 'to-do' list dashboard of the app when users open it so they'll see it every time they open the app regardless of the prompt; (iii) Encourage two recalls of Intake24 and wearing the device with a small payment (£5 as points); (iv) Provide feedback after each Intake24 recall	HUL
Before the trial (triggered)	Baseline phase	Extend the baseline phase to up to 2 weeks if users are slow to provide their data	HUL

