2.4 Sample size and minimum detectable size

2.4.1 Summary

The trial will adopt **a household-level randomisation**, with a target sample size of **around 4,200 participants** (2,100 in the control arm, 700 per intervention arm) at the final data collection point (**5 months after the randomisation**) to be powered to detect effect sizes deemed substantive from previous literature (see Section 2.4.2.2 Table 5). We expect users to come from ~2,300 households based on the demographic profile of Wolverhampton LA (see Appendix B).

To achieve a post-attrition sample of 4,200 participants, HUL expects to recruit a sample of around **25,800 participants** at the beginning of the baseline stage, given the attrition rate at various trial stages estimated by HUL (see Section 2.4.2.3 Table 6).

BIT has conducted power calculations for the primary research question "Does the incentive scheme improve physical activity (PA) and diet at the five month mark?". The power calculations focus on the primary outcomes. The primary analysis pools all the treatment arms together and assesses their overall difference against the control.

Given the post-attrition sample size of 4,200 participants, the minimum effect sizes we are powered (at 80% level) to detect at the 5-month's mark in the primary analysis are:

Physical activity primary outcomes:

- Daily MVPA (min/day): 2.4 min/day
- Daily steps: 371 steps/day

Dietary primary outcomes:

- Fruit and vegetables (g/day): 18.7 g/day
- Fibre (g/day): 0.74 g/day
- Free sugars (% food energy): 0.63%
- Saturated Fat (% food energy): 0.31%

The following subsections provide details on the key assumptions and decisions made concerning the power calculation. First, we provide the minimum required sample size at the analysis stage (post-attrition) given the target effect sizes for the primary outcomes (see Table 5). Then, we show the minimum required sample size at the recruitment stage (pre-attrition) given the predicted attrition rate at various stages (see Table 6) based on HUL's estimations. Last, we calculate the minimum detectable effect size for primary outcomes (see Table 7) based on the target sample size confirmed as feasible for this project by HUL and DHSC.

For further information on specific assumptions behind household-level randomisation, multiple-comparisons-adjustment, inclusion of covariates, and allocation ratio among trial arms, please see Appendix B.

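### Section 2.2.2.1 counts the 25,800 recruitment target at the start of onboarding, but Section 2.4 needs 25,800 at the start of baseline

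*Protocol*

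**What the plan says.** Protocol Section 2.2.2.1 (Recruitment target and timeline) gives the delivery partner's aim: "HUL aims at having about 25,800 users starting the onboarding phase". It refers the reader to the power calculation in Section 2.4. Its next sentence defines the stage: "During the onboarding phase, a user downloads the app, signs up, and provides consent to participate in the study". The same section says that uptake will be evaluated in week 6 to decide on a two-week extension. It also says that anyone who has not finished onboarding when the window closes cannot take part.

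Section 2.4.1 (Summary) places the same figure later, "at the beginning of the baseline stage, given the attrition rate at various trial stages estimated by HUL". Section 2.4.2.3 records 25,800 at the start of the baseline phase as the number agreed with the funder. The first column of Table 6 is headed accordingly, and its note gives 40% attrition between baseline and randomisation in every arm.

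The protocol separates the two stages. Section 2.2.2.3 says that once a user has consented, registered and "confirmed they meet the eligibility criteria, their onboarding phase ends and their baseline phase starts". Section 2.2.3 agrees about the baseline period: "It starts the day the user has been positively assessed for eligibility". Users are removed in between. Section 2.2.2.2 states: "Participants not providing informed consent will be excluded from the trial". Section 2.2.2.3 stops those who fail the age, residence or self-assessed suitability criteria. Footnote 11 in Section 2.2.3 adds a ceiling: "The app will limit the total number of registered users to 31,500".

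**The concern.** One number is attached to two different points in the user journey, and the earlier point sits in the section that sets the recruitment target. Users who decline consent, prove ineligible, abandon sign-up or run out of time would all count towards 25,800 onboarding starts, yet none would enter the first column of Table 6. Section 2.2.3 names two routes to too few randomised participants: missing the recruitment target, and more attrition in baseline than estimated. Loss during onboarding falls under neither if the target is counted at onboarding start.

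At stake is the 5-month sample of 4,200 on which the stated detectable effects rest. The reading of uptake at week 6 is also affected, because Section 2.2.2.1 contains that decision and gives no other uptake figure.

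**Working it through.** **Inputs (Protocol, Table 6 and Section 2.4.1).** Required at 5 months: 700 in each incentive arm and 2,100 in control. Attrition from randomisation to 5 months: 62% (high), 63% (medium), 69% (low), 78% (control). Attrition from baseline to randomisation: 40% in all arms.

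**Step 1: reproduce the plan's figure.** N randomised = N at 5 months / (1 − 5-month attrition). N at start of baseline = N randomised / (1 − 0.40). Each result is rounded up.

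| Arm | Randomised: computed (stated) | Baseline start: computed (stated) |
|---|---|---|
| High | 700/0.38 = 1,843 (~1,900) | 3,072 (~3,100) |
| Medium | 700/0.37 = 1,892 (~1,950) | 3,154 (~3,200) |
| Low | 700/0.31 = 2,259 (~2,250) | 3,765 (~3,800) |
| Control | 2,100/0.22 = 9,546 (~9,400) | 15,910 (~15,700) |
| Total | 15,540 (~15,500) | 25,901 (~25,800) |

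The total agrees within 0.4%, and the forward check gives 25,800 × 0.60 = 15,480. Table 6 is therefore sound, and 25,800 is a start-of-baseline number. The chain has no term for loss before baseline.

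**Step 2: count 25,800 at onboarding start instead.** Let f be the share lost between starting onboarding and starting baseline. The protocol does not give f, so the values below are assumptions.

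- Baseline starters = 25,800 × (1 − f)
- N at 5 months = 4,200 × (1 − f), with Table 6 rates unchanged
- Onboarding starts needed for 25,800 at baseline = 25,800 / (1 − f)
- Detectable effect for fruit and vegetables = 18.7 / √(1 − f) g/day, starting from the stated 18.7 at 4,200

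| f (assumed) | Baseline starters | N at 5 months | Onboarding starts needed | Detectable effect (g/day) |
|---|---|---|---|---|
| 10% | 23,220 | 3,780 | 28,667 | 19.7 |
| 20% | 20,640 | 3,360 | 32,250 | 20.9 |
| 30% | 18,060 | 2,940 | 36,857 | 22.4 |

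**Step 3: compare with the plan's own limits.** Table 2 moves the focus to 3 months if the 5-month sample is below 80% of 4,200, that is 0.80 × 4,200 = 3,360. This is reached exactly at f = 20% and crossed above it. The 21 g/day target in Table 5 is lost when 18.7/√(1 − f) exceeds 21, that is f above 1 − (18.7/21)² = 0.207, about 21%.

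**Step 4: the registration cap.** 1 − 25,800/31,500 = 0.181. The cap leaves room for 25,800 baseline starters only if at most about 18% are lost between registration and baseline. Section 2.2.2.2 places consent before registration, so refusals of consent should not use places under the cap.

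**The case against.** The strongest reply is that the operative target is clear. Section 2.4.2.3 records what was agreed, at the start of baseline and split by arm. Section 2.2.2.1 only refers to Section 2.4 and derives no competing number. The word onboarding is also used loosely elsewhere: Table 15 extends it to wearable connection, Intake24 and even randomisation. The phrase may therefore be a slip. It may well be, but it still needs correcting, because Section 2.2.2.1 defines the term in its very next sentence and Section 2.2.2.3 ends onboarding where baseline begins.

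A reader might infer that the week-6 extension would not be triggered. The documents do not support that. Section 2.2.2.1 says only that uptake will be evaluated, without naming the count. Section 2.2.3 measures trial entry at randomisation. The funnel report in Table 13 shows registered, consented and randomised users against target, daily during launch. Table 2 separately allows recruitment to be extended if necessary. A shortfall could therefore be seen by other routes. This objection stands. What remains is that no reported count sits at the point where Table 6 starts, and randomised counts lag because the baseline phase takes time.

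It is also fair that the loss rates are assumed, and that the delivery partner's acquisition plan, which is not at hand, may contain an estimate. A 10% loss would keep the detectable effect inside the 21 g/day target. The cap is 22% above 25,800 (31,500/25,800 = 1.22), so it permits over-recruitment, though it is a ceiling and not a planned allowance.

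**Conclusion.** The contradiction holds. The recruitment target is stated one stage too early in Section 2.2.2.1. Meeting it literally would leave the 5-month sample short of 4,200 by the proportion lost in onboarding. The size is unknown because the protocol gives no such proportion. The table above is illustrative and assumes that Table 6 rates apply unchanged to those who reach baseline.

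Three stronger readings should not be drawn. Table 6 is not miscalculated. The trial is not shown to be underpowered, since the target in Section 2.4 is correct and the 80% threshold is crossed only if more than 20% are lost. The final sample is not short by one person for each user lost in onboarding: that one-for-one count applies at the start of baseline, and at 5 months it is about 0.16 of it (4,200/25,800). On week 6, the most that can be said is that an onboarding-start count might mask a shortfall, partly offset by the consented and randomised counts already reported.

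**What to change.** In Section 2.2.2.1, restate the target as about 25,800 users who have passed eligibility and started baseline, in line with Section 2.4. State that week-6 uptake is judged against that count, and add the count to the existing funnel report in Table 13. Check the 31,500 cap in footnote 11 against the loss expected between registration and baseline; if more than about 18% is expected, the cap and the target do not fit together.

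The cost is a change of wording and one extra count on a live dashboard. Progress at week 6 will look less favourable than on onboarding starts. Table 6, the power calculation and the 4,200 target stay as they are.

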2.2.2.2 Providing informed consent

After an initial set of app-orientation screens explaining what the app is about, participants provide informed consent to participate in the study. As part of the consent process, interested users will be asked to read a participant information sheet and agree (or not agree) to:

• Take part in a study in which they will be randomly allocated to a control or a financial incentive intervention.

- Being contacted for research purposes (e.g. interviews being conducted as part of the implementation and process evaluation).
- Have their data shared with BIT to allow for data analysis.

Participants not providing informed consent will be excluded from the trial. Consent forms will be provided as part of the documentation for the ethical approval process. Consented users are subsequently asked to confirm they are over 18 years old and to the privacy notice and Terms of Service relating to the app. They may also optionally subscribe to 'reminder' emails from the app about their progress and other features. Users may unsubscribe from these communications at any time in the app.

2.2.2.3 Registration process

Participants will then be prompted to register their details on the app using one of the NHSX-approved authentication methods (Apple ID, Facebook, Google or email / password). To mitigate fraud risk, the app also requires participants to confirm their phone number via a One-Time Password (OTP).

At the second stage of registration, participants will be asked to enter mandatory information, including full name, date of birth, self-reported height, self-reported weight, gender, ethnicity, and postcode (full address). Once registered and logged-in to the app, they will also be asked to enter non-mandatory information, including education, motivations to change, and disability status.

Participants will be considered eligible if they meet the following criteria:

(i) geographic criteria (resident in Wolverhampton)

(ii) age criteria (18+ years old)

Those that are non-eligible will not be granted further access to the app, instead they will be signposted to relevant services where applicable. Please see **HUL's intervention design plan** for more detail. The app will show participants information on eligibility criteria and ask them to self-assess whether they are eligible to participate. Participants will be informed that the app provides general health information to encourage a healthy lifestyle.

During the sign-up process, participants will be asked to confirm they have read and understood the eligibility information and whether the pilot is suitable for them. The app will advise that prospective participants should contact a health professional if they have any concerns about using the app. The app may not be suitable for people who have (or have had) eating disorders or any other condition which may affect someone's ability to change their diet or physical activity behaviours. Users should only sign up to the app if they, and their health professional if appropriate, agree that the app is suitable for their use to ensure that the app will be used safely.

The eligibility criteria that participants need to self-assess against a clear list of eligibility criteria to use the app (and therefore be enrolled in the study). The eligibility criteria is set out in **Appendix I Eligibility_Screening criteria_V6.1**.

If participants' self-assessment indicates that they are eligible, they will proceed to the second stage of screening, otherwise their sign-up will end and they will not be able to use the app further, nor be included in the trial. Once a participant has provided informed consent, registered, and confirmed they meet the eligibility criteria, their onboarding phase ends and their baseline phase starts, which is elaborated in the next section.

